4.1 Inclusion Criteria

4.1.1 Age: Patients must be \geq 12 months and \leq 21 years of age at the time of study enrollment.

4.1.2 Diagnosis:

Part A: Patients with recurrent or refractory non-CNS solid tumors are eligible. Patients must have had histologic verification of malignancy at original diagnosis or relapse except patients with extra-cranial germ-cell tumors who have

THIS PROTOCOL IS FOR RESEARCH PURPOSES ONLY, SEE PAGE 1 FOR USAGE POLICY

elevations of serum tumor markers including alpha-fetoprotein or beta-HCG. Patients in Part A cannot have CNS metastases.

Part B: Patients with recurrent or refractory CNS tumors will be eligible and must have a histological verification of malignancy at original diagnosis or relapse except in patients with intrinsic brain stem tumors, optic pathway gliomas, or patients with CNS-germ cell tumors and elevations of CSF or serum tumor markers including alpha-fetoprotein or beta-HCG.

4.1.3 **Disease Status:** Patients must have either measurable or evaluable disease (see Sections [12.2](#) and [12.3](#) for definitions).

4.1.4 **Therapeutic Options:** Patient's current disease state must be one for which there is no known curative therapy or therapy proven to prolong survival with an acceptable quality of life.

4.1.5 **Performance Level:** Karnofsky $\geq 50\%$ for patients > 16 years of age and Lansky ≥ 50 for patients ≤ 16 years of age (See [Appendix I](#)). Note: Neurologic deficits in patients with CNS tumors must have been relatively stable for at least 7 days prior to study enrollment. Patients who are unable to walk because of paralysis, but who are up in a wheelchair, will be considered ambulatory for the purpose of assessing the performance score.

4.1.6 **Prior Therapy**

4.1.6.1 Patients must have fully recovered from the acute toxic effects of all prior anti-cancer therapy.

- Myelosuppressive chemotherapy:** At least 21 days after the last dose of myelosuppressive chemotherapy (42 days if prior nitrosourea).
- Hematopoietic growth factors:** At least 14 days after the last dose of a long-acting growth factor (e.g. Neulasta) or 7 days for short-acting growth factor. For agents that have known adverse events occurring beyond 7 days after administration, this period must be extended beyond the time during which adverse events are known to occur. The duration of this interval must be discussed with the study chair.
- Biologic (anti-neoplastic agent):** At least 7 days after the last dose of a biologic agent. For agents that have known adverse events occurring beyond 7 days after administration, this period must be extended beyond the time during which adverse events are known to occur. The duration of this interval must be discussed with the study chair.
- Immunotherapy:** At least 42 days after the completion of any type of immunotherapy, e.g. tumor vaccines.
- Monoclonal antibodies:** At least 3 half-lives of the antibody after the last dose of a monoclonal antibody. (See table on DVL homepage listing monoclonal antibody half-lives.)
- XRT:** At least 14 days after local palliative XRT (small port); At least 150 days must have elapsed if prior TBI, craniospinal XRT or if $\geq 50\%$ radiation of pelvis; At least 42 days must have elapsed if other substantial BM radiation.

THIS PROTOCOL IS FOR RESEARCH PURPOSES ONLY, SEE PAGE 1 FOR USAGE POLICY

- g. Stem Cell Infusion without TBI: No evidence of active graft vs. host disease and at least 84 days must have elapsed after transplant or stem cell infusion.
- h. Patients must not have received prior exposure to ramucirumab.

4.1.7 Organ Function Requirements

4.1.7.1 Adequate Bone Marrow Function Defined as:

- a. For patients with solid tumors without known bone marrow involvement:
 - Peripheral absolute neutrophil count (ANC) $\geq 1000/\text{mm}^3$
 - Platelet count $\geq 100,000/\text{mm}^3$ (transfusion independent, defined as not receiving platelet transfusions for at least 7 days prior to enrollment)
 - Hemoglobin $\geq 8.0 \text{ g/dL}$ at baseline (may receive RBC transfusions)
- b. Patients with known bone marrow metastatic disease will be eligible for study provided they meet the blood counts in 4.1.7.1.a (may receive transfusions provided they are not known to be refractory to red cell or platelet transfusions). These patients will not be evaluable for hematologic toxicity. At least 5 of every cohort of 6 patients must be evaluable for hematologic toxicity for the dose-escalation part of the study. If dose-limiting hematologic toxicity is observed, all subsequent patients enrolled must be evaluable for hematologic toxicity.

4.1.7.2 Adequate Renal Function Defined as:

- Urine protein: $\leq 30 \text{ mg/dL}$ in urinalysis or $\leq 1+$ on dipstick, unless quantitative protein is $< 1000 \text{ mg}$ in a 24 h urine sample.
- Creatinine clearance or radioisotope GFR $\geq 70 \text{ ml/min}/1.73 \text{ m}^2$ or
- A serum creatinine based on age/gender as follows:

Age	Maximum Serum Creatinine (mg/dL)	
	Male	Female
1 to < 2 years	0.6	0.6
2 to < 6 years	0.8	0.8
6 to < 10 years	1	1
10 to < 13 years	1.2	1.2
13 to < 16 years	1.5	1.4
$\geq 16 \text{ years}$	1.7	1.4

The threshold creatinine values in this Table were derived from the Schwartz formula for estimating GFR (Schwartz et al. J. Peds, 106:522, 1985) utilizing child length and stature data published by the CDC.

4.1.7.3 Adequate Liver Function Defined as:

- Bilirubin (sum of conjugated + unconjugated) $\leq 1.5 \times$ upper limit of normal (ULN) for age
- SGPT (ALT) $\leq 110 \text{ U/L}$. For the purpose of this study, the ULN for SGPT is 45 U/L.

THIS PROTOCOL IS FOR RESEARCH PURPOSES ONLY, SEE PAGE 1 FOR USAGE POLICY

- Serum albumin ≥ 2 g/dL.

4.1.7.4 Adequate Cardiac Function Defined As:

- Shortening fraction of $\geq 27\%$ by echocardiogram, or
- Ejection fraction of $\geq 50\%$ by gated radionuclide study.

4.1.7.5 Adequate Blood Pressure Control Defined as:

A blood pressure (BP) \leq the 95th percentile for age, height, and gender ([Appendix VIII](#)) measured as described in [Section 6.4](#), and not receiving medication for treatment of hypertension. Please note that 3 serial blood pressures should be obtained and averaged to determine baseline BP.

4.1.7.6 Adequate Coagulation Defined as:

- INR ≤ 1.5

4.1.8 Informed Consent: All patients and/or their parents or legally authorized representatives must sign a written informed consent. Assent, when appropriate, will be obtained according to institutional guidelines.

4.1.9 Tissue blocks or slides must be sent per [Section 8.10](#). If tissue blocks or slides are unavailable, the study chair must be notified prior to enrollment.

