4.0 PATIENT ELIGIBILITY

All clinical and laboratory studies to determine eligibility must be performed within 7 days prior to enrollment unless otherwise indicated. Laboratory values used to assess eligibility must be no older than seven (7) days at the start of therapy. Laboratory tests need **not** be repeated if therapy starts **within** seven (7) days of obtaining labs to assess eligibility. If a post-enrollment lab value is outside the limits of eligibility, or laboratory values are older than 7 days, then the following laboratory evaluations must be re-checked within 48 hours prior to initiating therapy: CBC with differential, bilirubin, ALT (SGPT) and serum creatinine. If the recheck is outside the limits of eligibility, the patient may not receive protocol therapy and will be considered off protocol therapy. Imaging studies, bone marrow biopsy and/or aspirate must be obtained within 14 days prior to start of protocol therapy (repeat the tumor imaging if necessary).

Clarification in timing when counting days: As an example, please note that if the patient's last day of prior therapy is September 1st, and the protocol requires waiting at least 7 days for that type of prior therapy, then that patient cannot be enrolled until September 8th.

Important note: The eligibility criteria listed below are interpreted literally and cannot be waived (per COG policy posted 5/11/01). All clinical and laboratory data required for determining eligibility of a patient enrolled on this trial must be available in the patient's medical or research record which will serve as the source document for verification at the time of audit.

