11.0 STATISTICAL AND ETHICAL CONSIDERATIONS

11.1 Sample Size and Study Duration

The study will be completed in 2 parts. Part A will be a dose-escalation phase including patients with non-CNS solid tumors, and Part B will include a safety and imaging evaluation in patients with CNS tumors.

THIS PROTOCOL IS FOR RESEARCH PURPOSES ONLY, SEE PAGE 1 FOR USAGE POLICY

A minimum of 2 evaluable patients will be entered at each dose level for determination of MTD. Once the MTD or recommended Phase 2 dose has been defined, up to 6 additional patients with recurrent or refractory solid tumors without restrictions on hematologic evaluable may be enrolled to acquire PK data in a representative number of young patients (e.g. six patients < 12 years old and six patients \geq 12 years old). Review of the enrollment rate into previous COG new agent studies indicates that 1-2 patients per month are available. The anticipated maximum number of evaluable subjects required to complete Part A is 24 patients. Assuming a 20% inevaluable rate, 29 patients may be enrolled and the study would be expected to be completed within 15-29 months. A maximum of 51 patients may be required in the unlikely event that each of the three dose levels are expanded to 12 because two DLTs of different types are observed at each of the three dose levels, 6 additional patients are needed for PK analysis, and a 20% inevaluable rate. The maximum of 51 would be completed within 26-51 months.

Part B of the study will require up to 6 evaluable patients enrolled at the MTD or RP2D as determined in Part A. Allowing for 20% inevaluability, 8 patients may be enrolled, and this would be expected to be completed within 4-8 months. If Part B is expanded to 12 because of two different classes of DLTs, then up to 15 patients could be enrolled. The maximum of 15 patients is expected to be completed within 8-15 months.

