11.2.2 Maximum Tolerated Dose

- The MTD will be the maximum dose at which fewer than one-third of patients experience DLT (See [Section 5.5](#)) during Cycle 1 of therapy.
- In the event that two DLTs observed out of 6 evaluable patients are different classes of Adverse Effects (e.g. hepatotoxicity and myelosuppression), expansion of the cohort to 12 patients will be considered if all of the following conditions are met:
 - One of the DLTs does not appear to be dose-related
 - The Adverse Effects are readily reversible
 - The study chair, DVL statistician, DVL committee chair or vice chair, and IND sponsor all agree that expansion of the cohort is acceptable

If fewer than 1/3 of patients in the expanded cohort experience dose-limiting toxicities, the dose escalation can proceed.

THIS PROTOCOL IS FOR RESEARCH PURPOSES ONLY, SEE PAGE 1 FOR USAGE POLICY

- The DLTs observed in the pharmacokinetic (PK) expansion cohort will be counted towards the total number of DLTs observed at the MTD during the dose escalation portion of the study. If $\geq 1/3$ of the cohort of patients at the MTD (during the dose escalation plus the PK expansion) experience DLT then the MTD will be exceeded.

11.2.3 Recommended Phase 2 Dose (RP2D):

After accrual to dose level 2 is completed, PK comparisons from dose levels 1 and 2 will be performed. An expansion cohort will accrue at the lowest tolerable dose at which C_{min} of ≥ 50 μ g/mL has been achieved in at least 5 out of 6 evaluable patients to acquire PK data in a representative number of young patients (i.e. patients < 12 years old). If at least 10 out of the total 12 evaluable patients have a steady state concentration of ramucirumab greater than 50 μ g/mL, then the RP2D has been defined. If $C_{min,ss}$ of ≥ 50 μ g/mL has not been achieved in at least 5 out of 6 evaluable patients from dose level 2, and if the MTD has not yet been reached, then dose level 3 will be considered.

11.3 **Dose Escalation and Determination of MTD**

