11.6 Statistical methods

11.6.1 **Analysis Sets**

Safety Analysis Set (SAS) will consist of subjects who receive any amount of study drug.

11.6.2 **Dose Evaluable Set (DES)** will consist of: 1) subjects who receive any amount of study drug and then experience DLT during Cycle 1; and 2) subjects who receive at least 85% of the prescribed dose in Cycle 1 and have an adverse event assessment in the first cycle. DES will be used for evaluation of each dose level for dose-escalation.

11.6.3 **Pharmacokinetic Analysis Set (PAS)** will include subjects who have sufficient PK data to derive at least one PK parameter.

11.6.4 **Efficacy Analyses:**

Preliminary efficacy analyses will also be performed by dose cohort for the Safety Analysis Set. Data cut-off for primary study analysis will occur when all enrolled subjects have completed 6 cycles of treatment or discontinued study drug administration. After the final analysis, additional analyses may be performed as appropriate.

11.6.5 **Pharmacokinetic Analyses**

Serum concentrations of Ramucirumab will be tabulated and summarized by dose level and time. Ramucirumab PK parameters will be derived from serum concentrations by non-compartmental analyses using actual times. Minimally, the following PK parameters will be calculated: C_{max} , t_{max} , and $AUC (t_{1/2}, CL, and Vd_{ss})$ will be calculated only if the data permit). Additional analysis utilizing the population pharmacokinetic approach may also be conducted if deemed appropriate.

11.6.6 **Immunogenicity Analyses**

Immunogenicity incidence will be tabulated, and correlation of immunogenicity to ramucirumab drug level, activity, and safety will be assessed as appropriate.

11.6.7 **Statistical Analyses**

Baseline demographics and baseline disease characteristics will be summarized for all enrolled patients who had at least one dose of study therapy.

Listing of patients including those treated at the MTD will be generated.

Treatment-emergent CTCAEs will be summarized by each dose level and for

THIS PROTOCOL IS FOR RESEARCH PURPOSES ONLY, SEE PAGE 1 FOR USAGE POLICY

overall population by each CTCAE grade separately.

Best overall response, duration of response, and duration of stable disease will also be summarized descriptively by each dose level.

Listing of deaths on study or 30 day post-discontinuation will be provided. Listing of SAEs will also be produced. Listing of AEs leading to treatment discontinuation will be provided.

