#### Part A:

A minimum of 2 evaluable patients will be entered at each dose level for determination of MTD. Once the MTD or RP2D has been defined, up to 6 additional patients with recurrent or refractory solid tumors without restrictions on hematologic evaluability may be enrolled to acquire PK data in a representative number of young patients. The anticipated maximum number of evaluable subjects required to complete Part A is 24 patients. Assuming a 20% inevaluable rate, 29 patients may be enrolled.

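### Patients with marrow disease cannot be scored with a myelosuppression DLT, yet they count as DLT-free in the pooled one-third test, and the expansion cohort has no limit on their number

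*Protocol*

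**What the plan says.** Protocol 4.1.7.1b admits patients with known bone marrow metastases and adds: "These patients will not be evaluable for hematologic toxicity". It then sets two safeguards. The first is confined to escalation: "At least 5 of every cohort of 6 patients must be evaluable for hematologic toxicity for the dose-escalation part of the study". The second names no part of the study: "If dose-limiting hematologic toxicity is observed, all subsequent patients enrolled must be evaluable for hematologic toxicity". Section 4.0 says of the criteria as a whole: "The eligibility criteria listed below are interpreted literally and cannot be waived".

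For the PK expansion, Protocol 11.1 says "up to 6 additional patients with recurrent or refractory solid tumors without restrictions on hematologic evaluable may be enrolled". SAP 5.2 (Part A) agrees: "solid tumors without restrictions on hematologic evaluability may be enrolled to acquire PK data in a representative number of young patients". Neither makes an exception for an earlier hematologic DLT.

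On counting, Protocol 11.2.2 states: "The DLTs observed in the pharmacokinetic (PK) expansion cohort will be counted towards the total number of DLTs observed at the MTD". It declares the MTD exceeded if one-third or more of the escalation and expansion patients combined have a DLT. The Dose Evaluable Set (11.6.2) takes anyone with a Cycle 1 DLT, plus "subjects who receive at least 85% of the prescribed dose in Cycle 1 and have an adverse event assessment in the first cycle". The SAP's DLT-evaluable population (Section 6) is defined in the same way. Neither definition mentions hematologic evaluability.

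Section 5.5.2 has two lists. The events in 5.5.2.1 (prolonged Grade 4 neutropenia, low platelets or platelet transfusion, cycle delay from myelosuppression) count only in hematologically evaluable patients. The events in 5.5.2.2 (arterial and venous thromboembolism, thrombosis needing anticoagulation, Grade 3 or worse hemorrhage) carry no such condition.

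**The concern.** A marrow-involved patient who completes Cycle 1 adds one to the denominator of the one-third test but can never add a 5.5.2.1 event to the numerator. The protocol recognizes this in escalation, where it tolerates at most one such patient in six. It drops that limit in the expansion, yet pools the expansion into the same MTD test. For myelosuppression, the reported DLT fraction at the recommended dose would then mix patients who were at risk with patients who were not, and a reader could not separate them.

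A second problem concerns enrollment. Once a dose-limiting hematologic toxicity has been seen, the second safeguard in 4.1.7.1b and the sample-size text give different answers on whether a marrow-involved patient may join the expansion.

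**Working it through.** **1. The plan's own figures.** Three dose levels of 6 plus 6 expansion patients give 3 × 6 + 6 = 24 evaluable, and 24 × 1.2 = 28.8, rounded up to the stated 29. The worst case is 3 × 12 + 6 = 42, and 42 × 1.2 = 50.4, rounded up to the stated 51. Nothing below alters these. The documents give no operating characteristics for the one-third test.

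**2. The threshold.** At the recommended dose the pooled cohort is normally 6 + 6 = 12, so the test needs 12/3 = 4 DLTs.

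**3. What that asks of evaluable patients.** Suppose all 6 escalation patients and k of the 6 expansion patients are hematologically evaluable. Considering 5.5.2.1 DLTs alone, the share of evaluable patients who must have one before the test fires is 4/(6 + k): 33% at k = 6, 36% at 5, 40% at 4, 44% at 3, 50% at 2 and 67% at 0.

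**4. Example.** One of 6 in escalation plus 2 of 3 evaluable in the expansion is 3/9 = 33% of evaluable patients, which meets one-third. The plan counts 3/12 = 25%, and the MTD is not exceeded.

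**5. Chance that the test fires.** Assumptions, none of them from the documents: one 5.5.2.1 DLT among the first 6, no DLT of any other kind, and true myelosuppression DLT rate p. With all 12 in the denominator, 3 more DLTs are needed from k patients, so the chance is P(Bin(k, p) ≥ 3). Over evaluable patients only, the total needed is (6 + k)/3, rounded up. At p = 1/3:

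| k | Total needed, all 12 | Chance | Total needed, evaluable only | Chance |
|---|---|---|---|---|
| 6 | 4 | 0.320 | 4 | 0.320 |
| 5 | 4 | 0.210 | 4 | 0.210 |
| 4 | 4 | 0.111 | 4 | 0.111 |
| 3 | 4 | 0.037 | 3 | 0.259 |
| 2 | 4 | 0 | 3 | 0.111 |

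Two effects are mixed in the fall from 0.320. At k = 5 or 4 the total needed is 4 under either denominator, so the drop comes only from having fewer patients at risk. At k = 3 or 2 the denominator itself matters: 0.037 against 0.259, and 0 against 0.111.

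At p = 0.25 the all-12 chances are 0.169 (k = 6), 0.051 (k = 4) and 0.016 (k = 3). At p = 0.10 they are 0.016, 0.004 and 0.001.

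**6. The enrollment texts side by side.** The 5-of-6 sentence in 4.1.7.1b is limited to escalation. The sentence after it is not limited, and Section 4.0 forbids waivers. Section 11.1 and SAP 5.2 lift all restriction on hematologic evaluability for the expansion. The first text bars a marrow-involved patient after a hematologic DLT, and the second admits the same patient.

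**The case against.** The strongest reply is that the calculation in step 5 starts from a hematologic DLT in escalation, which is exactly the event that triggers the second safeguard. If that safeguard reaches the expansion, no marrow-involved patient enrolls afterwards and there is no dilution. If it covers escalation only, as its neighboring sentence suggests, there is no contradiction. This stands as a limit on the table: the rows with k below 6 arise only if 11.1 prevails. It does not remove the point. Before any hematologic DLT is seen, 4.1.7.1b bars nobody from the expansion under either reading, and patients already enrolled stay in the denominator.

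Several stronger readings are tempting, but the documents do not support them.

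- A reader might infer that every hematologic DLT is diluted. The 5.5.2.2 events count in all patients. These include the vascular and bleeding events that the protocol stresses for this agent: Section 2.3.1 lists hypertension and deep vein thrombosis as the adult DLTs.
- A reader might infer that every expansion patient counts. Under 11.2.1, those who receive less than 85% of the dose for reasons other than toxicity and have no DLT are replaced. Expansion patients without marrow disease remain hematologically evaluable.
- A reader might infer that the reported fraction at 12 mg/kg is biased. The documents report neither a marrow-involved expansion patient nor a hematologic DLT.

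The rates of 1/3 and 0.25 may also be high. Section 9.1.8 puts neutropenia at 4–20% in single-agent trials, while a DLT needs Grade 4 neutropenia for more than 7 days. There is no pediatric experience to draw on (2.4.1). Low counts also remain visible elsewhere, through adverse events by grade (SAP 6.7.2) and laboratory shifts (SAP 6.7.4).

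**Conclusion.** The point holds in a limited form. The pooled test has no hematologically evaluable denominator for 5.5.2.1 DLTs, so the myelosuppression DLT fraction at the recommended dose is understated whenever DLT-evaluable, marrow-involved patients are in it. The example of 33% counted as 25% shows that this can cross the one-third line. How far it matters here depends on the number of such patients and the true DLT rate, and the documents give neither. At a true rate of 10% the test would hardly ever fire under either count.

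The disagreement between 4.1.7.1b and 11.1 with SAP 5.2 is a separate matter of wording, and it applies only after a hematologic DLT.

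This is a minor point. Section 5.3 reports escalation complete and the recommended dose set at 12 mg/kg. Nothing here shows that result to be wrong, and no sample-size figure changes. What remains open is how the DLT fraction is reported.

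**What to change.** In the SAP's DLT-evaluable population (Section 6) and in Protocol 11.2.2 and 11.6.2, state that 5.5.2.1 DLTs are also counted over patients evaluable for hematologic toxicity. Report that n/N beside the overall DLT n/N at each dose level.

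Reconcile the last sentence of 4.1.7.1b with Protocol 11.1 and SAP 5.2. Either make the unrestricted expansion subject to that sentence, or say that the sentence covers escalation only. Which reading was intended is for the study team to state.

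The cost is small. Marrow involvement is known at eligibility, and the study chair already enters evaluability and DLTs in the database (14.4.2). The change adds one table row. The drawback is a smaller denominator for that row and possibly a less favorable myelosuppression DLT rate. If no marrow-involved patient was enrolled at a dose, the two denominators will agree and the row will show it.

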5.2 Criteria for Starting Subsequent Cycles

A cycle may be repeated every 42 days if the patient has at least stable disease and has again met laboratory parameters as defined in the eligibility section, [Section 4.0](#).

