5.5.1.2 Dose-limiting hypertension

- Any Grade 4 hypertension
- A blood pressure > 25 mmHg above the 95th percentile for age, height, and gender ([Appendix VIII](#)) confirmed by repeated measurement is dose limiting.
- In patients who begin antihypertensive therapy a blood pressure > 10 mmHg but ≤ 25 mmHg above the 95th percentile for age, height, and gender ([Appendix VIII](#)) for > 14 days is dose limiting.

5.5.1.3 Non-hematological toxicity that causes a delay of ≥ 14 days between treatment cycles will be considered dose-limiting.

5.5.1.4 Proteinuria: Urine protein/creatinine (P/C) ratio > 1 and < 1.9 confirmed with a second measurement within 72 hours will be considered a DLT (See [Section 6.5](#))

5.5.1.5 Any gastrointestinal perforation event will be considered a DLT and require removal from protocol therapy.

5.5.1.6 Grade ≥ 2 wound complication or wound dehiscence will be considered a DLT and require removal from protocol therapy.

5.5.1.7 Grade ≥ 3 hepatic failure will be considered a DLT and require removal from protocol therapy.

5.5.1.8 Grade ≥ 2 reversible posterior leukoencephalopathy syndrome (RPLS) will be considered a DLT and require removal from protocol therapy.

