6.5 Dose Modifications for Proteinuria

If urinalysis shows \geq trace protein then obtain Urine Protein to Creatinine (UPC) concentrations (See [Appendix IX](#)).

Proteinuria: UPC Ratio	Action
If < 1	Continue protocol therapy
If 1-1.9	Hold next infusion. A second measurement should be obtained within 72 hours. A second confirmation of urine protein/creatinine (P/C) ratio 1-1.9 will be considered a DLT. If resolves to < 1 within 14 days, resume protocol therapy. Subsequent infusions will be given at a lower dose as outlined in Section 6.2 . Monitor the UPC weekly for 2 consecutive weeks once protocol therapy resumes. UPC ≥ 1 that persists ≥ 14 days will require removal from protocol therapy.
If > 1.9	Off protocol therapy

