9.1.5 Solution Preparation

Ramucirumab is compatible with common infusion containers. The use of a low protein binding 0.22 micron in-line filter is required. Aseptic technique is to be used when preparing and handling ramucirumab for infusion. Drug doses should be adjusted based on actual weight measured within 7 days prior to the beginning of each cycle. Based on the calculated volume of ramucirumab, add (or remove from pre-filled [with 0.9% normal saline] I.V infusion container) a sufficient quantity of sterile normal saline (0.9% weight/volume) to the container to a concentration > 0.4 mg/mL by making the total volume 100 mL for patients weighing 8-25 kg, and total volume 250 mL for patients weighing > 25 kg. For patients < 8 kg total volume should be at least 50 mL and concentration should be > 0.4 mg/mL. Do not use dextrose containing solutions. The container should be gently inverted to ensure adequate mixing.

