APPENDIX IX: URINE PROTEIN TO CREATININE (UPC) RATIO**Clinical Meaning of UPC**

There is a good correlation between the ratio of urine protein to creatinine concentrations (UPC) in a random urine sample and the amount of protein excreted in a 24-hour urine collection period.⁸³ Thus, the UPC allows for an estimation of the 24-hour urine protein excretion from a random sample. The creatinine excretion is fairly constant throughout the day regardless of changes in urine flow rate:

- Men excrete 20 mg to 25 mg of creatinine/kg of body weight/day
- Women excrete 15 mg to 20 mg of creatinine/kg of body weight/day
- Normal protein excretion is <100 mg to 150 mg per 24 hours.
- The UPC ratio is roughly equal to the 24 hour urine protein excretion in g/day

Calculating UPC Ratio

UPC ratio = (Urine protein [mg/dL]) / (urine creatinine [mg/dL]) = numerically equivalent to grams (g) protein excreted in urine over 24 hours.

Example: If a subject has a urine protein of 90 mg/dL and urine creatinine of 30 mg/dL,

$$\text{then UPC ratio} = \frac{90 \text{ (mg/dL)}}{30 \text{ (mg/dL)}} = 3$$

Result UPC is 3 correlating to roughly 3g of protein excretion in a 24-hour period.

Units for UPC ratio

UPC is a calculated ratio. The guidelines in the protocol are based on having urine protein and urine creatinine measured in the same units (e.g., mg/dL). The SI units for urine protein and urine creatinine are not the same, so these must be converted to mg/dL before calculating the ratio. For reference, the conversion factors for commonly used units for protein and creatinine are provided below.

Starting units	Conversion to mg/dL
Protein (g/L)	Multiply by 100
Creatinine (μmol/L)	Divide by 88.4
Creatinine (mmol/L)	Multiply by 11.3

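### Eligibility caps urine protein as a fixed 24-hour mass while the on-study rules use the UPC ratio, so a small child can be eligible at a baseline value that Sections 5.5.1.4 and 6.5 treat as a DLT, hold or removal

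*Protocol*

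**What the plan says.** **Eligibility.** Protocol Section 4.1.7.2 sets a urinalysis or dipstick limit "on dipstick, unless quantitative protein is" under 1000 mg in a 24-hour collection. A child who fails the spot test can therefore still enrol. The cap is the same for every patient. Section 4.1.1 enrols from 12 months up to 21 "years of age at the time of study enrollment". Section 9.1.5 specifies "total volume 100 mL for patients weighing 8-25 kg" and has a separate instruction for patients under 8 kg, so very small patients are expected.

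**On-study rules.** These use the UPC ratio.
- Section 5.5.1.4: a UPC above 1 and below 1.9 "confirmed with a second measurement within 72 hours will be considered a DLT".
- Section 6.5, UPC 1-1.9: the next infusion is held, and "A second confirmation of urine protein/creatinine (P/C) ratio 1-1.9 will be considered a DLT". In addition, "UPC ≥ 1 that persists ≥ 14 days will require removal from protocol therapy".
- Section 6.5, UPC above 1.9: off protocol therapy. Under Section 5.5.1.10, a possibly related toxicity that requires removal is also a DLT.

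Neither 5.5.1.4 nor 6.5 refers to the baseline value. Section 6.2.1 lets a patient with a non-hematological DLT continue once values are back at baseline, but it excepts what Section 6.5 provides.

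**Start of later cycles.** Section 5.2 requires that the patient "has again met laboratory parameters as defined in the eligibility section", which brings the 4.1.7.2 limit back at each cycle alongside 6.5.

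**Link between the two scales.** Appendix IX states: "The UPC ratio is roughly equal to the 24 hour urine protein excretion in g/day".

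**The concern.** If UPC and grams per day were interchangeable, the cap (under 1000 mg) and the DLT range (above 1) would meet without overlapping. They are interchangeable only for a patient who excretes about 1 g of creatinine a day, and a small child excretes much less. The same 24-hour protein then gives a much higher ratio, so a child can be eligible at a value for which the on-study rules already require a hold or removal.

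Two things are at stake. The first is consistency: following the text literally, a child could be dosed and then held or removed for a finding that was there at enrolment. The second is DLT counting. Section 5.5 asks only for possible attribution, proteinuria is a listed ramucirumab toxicity (Section 9.1.8), and Section 4.1.7.2 does not require a baseline UPC that could show that the value has not changed. In a group of six evaluable patients, one such count is 1/6, about 17 percentage points.

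**Working it through.** **Inputs.** Cap: 1000 mg/24 h (4.1.7.2). Action values: UPC 1 and 1.9 (5.5.1.4, 6.5). Creatinine excretion: 20-25 mg/kg/day for men and 15-20 for women (Appendix IX), so 15-25 overall. The documents give no paediatric rate, and applying this range to children is an assumption.

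**The plan's own figure.** Appendix IX's example is 90 mg/dL protein over 30 mg/dL creatinine: 90/30 = 3, which reproduces. It is read as about 3 g/day.

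**When that reading holds.** UPC = 24-hour protein (mg) / 24-hour creatinine (mg). It equals g/day only when creatinine is 1000 mg/day, which is a weight of 1000/25 = 40 kg, 1000/20 = 50 kg or 1000/15 = 66.7 kg. The equality therefore holds only at about 40-67 kg.

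**UPC at the cap** = 1000 / (weight × rate):

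| Weight | 25 mg/kg/day | 20 mg/kg/day | 15 mg/kg/day |
|---|---|---|---|
| 10 kg | 4.0 | 5.0 | 6.7 |
| 20 kg | 2.0 | 2.5 | 3.3 |
| 30 kg | 1.3 | 1.7 | 2.2 |
| 40 kg | 1.0 | 1.25 | 1.7 |
| 70 kg | 0.57 | 0.71 | 0.95 |

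**Weights at which the scales cross.** The cap exceeds UPC 1 below 40 kg at every rate in the range (below 66.7 kg at 15 mg/kg/day). It exceeds UPC 1.9 below 1000/(1.9 × 25) = 21.1 kg at every rate (below 1000/(1.9 × 15) = 35.1 kg at 15 mg/kg/day).

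**How much of the eligible range overlaps.** Protein at UPC 1 is weight × rate.
- 10 kg: 150-250 mg/day gives UPC 1, and 1.9 times that, 285-475 mg/day, gives UPC 1.9.
- 20 kg: 300-500 mg/day gives UPC 1, and 570-950 mg/day gives UPC 1.9.

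Protein below the first figure gives a UPC under 1, so only the upper part of the range under 1000 mg conflicts.

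**Sensitivity to the adult rates.** At an assumed 10 mg/kg/day the overlap widens: UPC 10 at the cap for a 10 kg child, with crossings at 100 kg (UPC 1) and 52.6 kg (UPC 1.9).

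**Start of a cycle.** The rules can also differ in the other direction. At 60 kg and UPC 0.9, Section 6.5 says to continue. Protein is 60 × 20 × 0.9 = 1080 mg/day at 20 mg/kg/day, over the cap, but 60 × 15 × 0.9 = 810 mg/day at 15, under it. This matters only if the spot test also fails and a 24-hour sample is taken, and the Section 8.1 schedule lists urinalysis, not a 24-hour collection.

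**Effect on a two-in-six reading (illustration only).** Assume an independent true DLT risk of 10%. The chance of two or more DLTs in six is 1 − 0.9^6 − 6 × 0.1 × 0.9^5 = 0.114. If one of the six is counted for baseline proteinuria, the chance of at least one more among five is 1 − 0.9^5 = 0.410. At 5% the pair is 0.033 and 0.226; at 20% it is 0.345 and 0.672.

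**The case against.** The strongest reply is that the plan has a filter. Every DLT must be at least possibly attributable to protocol therapy (Section 5.5). The study chair enters DLT evaluations, which are reviewed weekly with the statistician (Section 14.4.2). The SAP counts a treatment-emergent event only if it occurs or worsens after baseline (SAP 6.7.2). Urinalysis is done pre-study, footnote 5 of Section 8.1 mentions patients followed for prior proteinuria, and 6.5 calls for a UPC at trace protein or more, so a pre-dose UPC may well exist. Part A escalation is complete with the RP2D set at 12 mg/kg (Section 5.3.1).

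Much of this stands. Known, stable proteinuria need not be called a DLT, and the SAP definition protects the adverse event tables. But that definition does not govern the DLT decision, and 4.1.7.2 does not expressly require a baseline UPC. The hold and removal steps in 6.5 carry no attribution or baseline condition of their own.

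A reader might go further and infer that any small child admitted through the 24-hour exception is already in the DLT range, or that the Part A dose decision was distorted. The documents support neither. A child in the lower part of the range has a UPC under 1, and nothing in the documents says how many enrolled children had baseline proteinuria or whether any DLT arose this way.

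**Conclusion.** The point holds as a conflict between stated rules. Section 4.1.7.2 can admit a small child whose baseline UPC falls where 5.5.1.4 and 6.5 call for a hold, a DLT or removal, and no baseline provision resolves it. On the Appendix IX rates the overlap with UPC above 1 exists below 40 kg whichever rate in the range is used, and with UPC above 1.9 below about 21 kg. The exact weights depend on adult creatinine rates; the direction of the conflict does not.

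Hold or removal follows directly from the text. Counting as a DLT is only possible, because it depends on attribution. The frequency is unknown, so no effect on the trial's results can be sized. What remains exposed is Part B (up to 6 evaluable patients, up to 15 enrolled if expanded, Section 11.1) and the interpretation of any proteinuria DLT in Part A. The repair is cheap and should be made.

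**What to change.** Reconcile Sections 4.1.7.2, 5.2, 5.5.1.4, 6.5 and Appendix IX:

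1. Put the eligibility and on-study urine-protein rules on a consistent basis that is appropriate to body size.
2. State how proteinuria present at baseline is handled, both in the DLT definition and in the hold and removal rules.
3. State which single urine-protein rule governs the start of a cycle.
4. Restrict the g/day equivalence in Appendix IX to patients excreting about 1 g of creatinine per day.
5. When reporting Part A, give the baseline urine-protein finding beside any proteinuria DLT.

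The thresholds, and whether to reconcile through eligibility or through a baseline provision, are for the sponsor to decide. The cost is a short text amendment. UPC is already measured in this protocol. A change to eligibility might exclude a few small children; a baseline provision would need a pre-dose UPC in patients who fail the spot test.
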